6.15.2. Surveillance of Subsequent Treatment for Primary Disease

Throughout the survival surveillance period [See Section 6.15.3], the information of subsequent treatment for primary disease; e.g., antitumor chemotherapy, antitumor immunotherapy, radiotherapy, and hematopoietic stem cell transplant; including the name of medications, the date of treatment initiation and the tumor responses will be surveyed.

6.15.3. Survival Surveillance

A survival surveillance will be continued, at intervals of six months or less whenever possible, for up to 2 years from the date of initiation of investigational drug administration (Day 1 of Cycle 1) to confirm “survival” or “death” of subjects. When the subject’s death is confirmed, the “date of death” or “the most recent date (date of the last day) of survival confirmation” should be specified. The surveillance via telephone is allowed.

6.16. Pharmacokinetics

Pharmacokinetics (PK) assessment will be performed only in Cycle 1 only at the investigational sites where the principal investigator has agree to perform PK assessment in advance. The remaining portion of samples after the completion of determination of drug concentration will be appropriately discarded at a central laboratory.

6.16.1. Blood Collection for Determination of Drug Plasma Concentration

At the time points shown in Table 8, blood samples (approximately 10 mL containing ≥ 4 mL

of plasma) for determination of plasma drug concentration will be collected from a vein of forearm of the opposite arm of the infusion site. The collected blood samples will be processed at the investigational sites and then submitted to the central laboratory according to a specific procedure. The detailed procedures of blood collection, sample processing and submission are specified in a separate document, and will be provided to the investigational sites together with a set of sample collection kits including tubes for blood collections and containers for shipment.

At the central laboratory, plasma concentration of arsenic, darinaparsin and its metabolites will be analyzed. The results of analysis will be reported to the investigational sites by the Sponsor or CRO.

Table 8: Time Points of Blood Collection for Drug Plasma Concentration in Cycle 1

Time Point	Time window
Day 1: 0 hr after the start of investigational drug infusion,	Within 60 min prior to the start of infusion
1 hr (immediately after the end of infusion),	Within 15 min after the end of infusion
2 hrs (1 hr after the end of infusion),	± 15 min
4 hrs (3 hrs after the end of infusion),	± 15 min
6 hrs (5 hrs after the end of infusion),	± 30 min
8 hrs (7 hrs after the end of infusion).	± 30 min
Day 2: 0 hr	Within 60 min prior to the start of infusion
Day 3: 0 hr	
Day 4: 0 hr	
Day 5: 0 hr after the start of investigational drug infusion,	Within 60 min prior to the start of infusion
1 hr (immediately after the end of infusion),	Within 15 min after the end of infusion
2 hrs (1 hr after the end of infusion),	± 15 min
4 hrs (3 hrs after the end of infusion),	± 15 min
6 hrs (5 hrs after the end of infusion),	± 30 min
8 hrs (7 hrs after the end of infusion).	± 30 min
Day 6: Same time of the infusion start on Day 5	± 60 min
Day 8: Same time of the infusion start on Day 5	± 60 min
Day 15:	+ 6 days (Day 15 - 21)

6.16.2. Urine Collection for Determination of Drug Urine Concentration

At the time periods shown in Table 9, the entire urine will be accumulated in Cycle 1. The urine accumulation will be started after the subject completely urinates, and completed after the subject completely urinates during each time period of urine collection.

After the measurement of a total volume (mL) of urine collected at each time period, ≥ 20 mL of urine will be taken in the container and submitted to the central laboratory according to a specific procedure. The detailed procedures of urine collection, sample processing and submission are specified in a separate document, and will be provided to the investigational sites together with a set of sample collection kits including containers for shipment.

At the central laboratory, urine concentration of arsenic, darinaparsin and its metabolites will be analyzed. The results of analysis will be reported to the investigational sites by the Sponsor or CRO.

Table 9: Time Periods of Urine Collection for Drug Urine Concentration in Cycle 1

Time Periods			Time window
Day 1:	Start of urine accumulation	0 hr from the start of infusion	Within 60 min prior to the start of infusion ± 15 min
	~ End of urine accumulation	For 4 hrs (3 hrs after the end of infusion)	
	Start of urine accumulation	4 hr from the start of infusion	
Day 2:	~ End of urine accumulation	Until 24 hrs after the start of infusion on Day 1	Within 60 min prior to the start of infusion on Day 2
Day 5:	Start of urine accumulation	0 hr from the start of infusion	Within 60 min prior to the start of infusion ± 15 min
	~ End of urine accumulation	For 4 hrs (3 hrs after the end of infusion)	
	Start of urine accumulation	4 hr from the start of infusion	
Day 6:	~ End of urine accumulation	Until 24 hrs after the start of infusion on Day 5	± 60 min of same time of the infusion start on Day 5

6.17. Reference: Volume of Blood Sample Collection

As shown in Table 10, Table 11 and Table 12, the standard blood sample collection volume from the screening period to the end of Cycle 1 is 42-47 mL per subject who are not subject to drug plasma PK assessment and 222-227 mL per subject who are subject to the assessment. The standard volume in each cycle from Cycle 2 is 24 mL and 8 mL in the follow-up period. When a subject completes the study at the end of 6 cycles, the standard volume is approximately 170-175 mL in a subject who is not subject to drug plasma PK assessment and 350-355 mL in a subject who is subject to the assessment.

Table 10: Blood Sample Collection Volumes from Screening Period to Cycle 1

Test Items	Volume of Blood Sample Collection per Time Point (approximately)	Frequency	Subtotal Volume
Hepatitis virus	2-7 mL	x 1	2-7 mL
Hematology	2 mL	x 5	10 mL
Clinical chemistry	4 mL	x 5	20 mL
Blood coagulation	2 mL	x 5	10 mL
Determination of Drug Plasma Concentration	10 mL	x 18	180 mL
Total Volume	Blood Collection for Determination of Drug Plasma Concentration	No	42 - 47 mL
		Yes	222 - 227 mL

Table 11: Blood Sample Collection Volumes in Each Cycle from Cycle 2

Test Items	Volume of Blood Sample Collection per Time Point (approximately)	Frequency	Subtotal Volume
Hematology	2 mL	x 3	6 mL
Clinical chemistry	4 mL	x 3	12 mL
Blood coagulation	2 mL	x 3	6 mL
Total Volume			24 mL

Table 12: Blood Sample Collection Volumes in Follow-up Period

Test Items	Volume of Blood Sample Collection per Time Point (approximately)	Frequency	Subtotal Volume
Hematology	2 mL	x 1	2 mL
Clinical chemistry	4 mL	x 1	4 mL
Blood coagulation	2 mL	x 1	2 mL
Total Volume			8 mL

7. SAFETY DATA COLLECTION AND REPORTING

7.1. Definitions

7.1.1. Adverse Events

An adverse event (AE) is defined as “any untoward medical occurrence in a subject administered an investigational drug and which does not necessarily have a causal relationship with this treatment”.

This definition of AEs includes any such medical occurrences or exacerbation of pre-existing medical conditions or events (primary disease, underlying disease or concurrent diseases etc.). Obvious exacerbation of the pre-existing medical conditions; worsening in severity, increase in frequency, or extending of duration of the events, in the judgment of the principal investigator or sub-investigator, will qualify as an AE.

The principal investigator or sub-investigator will identify a “term” of diagnosis or syndrome of the AE as much as possible. Diseases or clinical signs with accompanying symptoms, the diseases or clinical signs will be identified and qualified as AEs.

The principal investigator or sub-investigator is responsible to confirm the changes in laboratory test results (vital signs, ECGs, laboratory test values, etc.) from baseline values in an individual subject. The clinically significant abnormal changes; including any change for which a new treatment or alternative treatment, in the judgment of the principal investigator or sub-investigator, will qualify as AEs. Diseases or clinical signs accompanying abnormal laboratory findings, the diseases or clinical signs will qualify as AEs.

7.1.2. Serious Adverse Events

A serious adverse event (SAE) is defined as an adverse event that

- is fatal
- is life threatening (an event that places the subject at immediate risk of death)
- requires inpatient hospitalization or prolongation of existing hospitalization
- results in persistent or significant disability/incapacity
- is a congenital anomaly/birth defect
- is any other medically important condition

A hospitalization meets the regulatory definition for “serious” is any inpatient hospital admission that includes a minimum of an overnight stay in a health care facility. A hospitalization only for the previously scheduled treatment or examination (operations or medical tests planned in advance) will not qualify as an AE.

Any AE that does not clearly meet one of the definitions above may be considered by the principal investigator or sub-investigator whether the event meets the criteria of “any other medically important condition” in the definitions of a SAE.

7.2. Procedures for Adverse Events Reporting

The principal investigator or sub-investigator (or designated staff) will collect and identify the following information on AEs during the period from the start of investigational drug administration to the end of follow-up period, and enter a description of the event into the eCRF.

- Term of adverse event
- Date of onset
- Seriousness; serious or not serious
- Severity
- Relationship to the investigational drug; if “No,” the reason for “No”
- Any action taken; if “Yes,” the details of the action
- Outcome and date of outcome confirmation (date of resolution, date of confirmation or examination of resolving/not resolved events, date of death, etc.)

Relationship (Causality)

Relationship of an AE to the investigational drug should be assessed from the point of view that “there is a reasonable possibility that the investigational drug caused the AE”. The principal investigator or sub-investigator should determine either of “Yes” or “No”.

Severity Assessment

Severity of an AE will be assessed by the principal investigator or sub-investigator, using the 5-grade scale according to NCI-CTCAE Version 4.0. For those events not found in NCI-CTCAE Version 4.0, the principal investigator or sub-investigator will clinically determine the severity based on the definition in Table 13.

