5.3.2. Administration

The investigational drug will be reconstituted and diluted according to the preparation procedures described in Section 5.2, and will be given intravenously over 1 hour (± 10 minutes) on each day of administration. After the infusion, a flushing with a sufficient amount of saline will be done to ensure all the drug remaining in the infusion route is infused fully to the subject.

Since the injection site abnormalities have been frequently reported in subjects who received the investigational drug via a peripheral line in the previous clinical studies, the

administration of the investigational drug is recommended to be given through the central vein (e.g., via an implantable subcutaneous infusion port, a central venous catheter, a peripherally inserted central venous catheter). If any abnormal finding at the injection site is observed during the infusion via a peripheral line, the administration will be held at the discretion of the principal investigator or sub-investigator. Saline may be infused via a three-way stopcock. The IV infusion may be given from another peripheral vein or via a central venous line or port.

The following matters should be noted when the investigational drug is administered:

- During the injection via a peripheral line, full care should be taken to avoid extravasation. If any extravasation is observed, the dose will be held immediately, medical procedures will be provided for it, and a change in the peripheral vein for IV infusion will be considered.
- No other drug for injection should be given concurrently via the same IV line.
- The investigational drug administration will be started at the same time as much as possible in subjects for pharmacokinetic assessment in Cycle 1 [See Section 6.16].

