6.12. Concomitant Medication/Procedures

Throughout the study period; from the day of obtaining the informed consent to the end of the follow-up period, the information listed below about concomitant medication or therapeutic procedures such as blood transfusion, wound care and oxygen inhalation will be collected.

However, the use of dilute solutions such as water for injection or saline; which are not intended for treatment; except for fluid therapy to prevent or correct problems with their fluid and/or electrolyte status, will not be determined as concomitant medication. The use of antiseptic solution, cleaning agent or heparin used for preventing blood coagulation (heparin lock) within a cannula/catheter placed in a peripheral vein; which do not have direct effect on the subject's body, will not be determined as concomitant medication. Blood transfusions should be determined as concomitant procedures.

- Medication / procedures
- Date started
- Date stopped
- Only for medication: total daily dose, unit and route
- Indication

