9.1.3. Safety Analysis Set

A group of subjects who receive at least one dose of investigational drug is defined as the "safety analysis set". The safety analysis set will be used for the analysis of safety endpoints.

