12.1.7 Number of Subjects with Any Grouping Adverse Event

The occurrence of AEs will be summarized by any grouping Adverse Event, preferred term according to the MedDRA dictionary, and by ethnic background and by severity. Grouping Adverse Event is following.

Grouped Term	Preferred Terms
Fatigue/malaise	Fatigue, Malaise
Hepatic function test abnormal	Aspartate aminotransferase increased, Alanine aminotransferase increased, Gamma-glutamyltransferase increased
Anaemia	Anaemia, Haemoglobin decreased
Thrombocytopenia	Thrombocytopenia, Platelet count decreased
Neutropenia	Neutropenia, Neutrophil count decreased
Lymphopenia	Lymphopenia, Lymphocyte count decreased
Leukopenia	Leukopenia, White blood cell count decreased
Injection site reaction	Infusion site pain, Injection site pain, Injection site reaction, Injection site rash, Infusion site pruritus, Infusion site rash
Hyperglycaemia	Hyperglycaemia, Blood glucose increased
Taste disorder	Taste disorder, Dysgeusia
Hyperbilirubinaemia	Hyperbilirubinaemia, Blood bilirubin increased
Hypoalbuminaemia	Hypoalbuminaemia, Blood albumin decreased
Hypomagnesaemia	Hypomagnesaemia, Blood magnesium decreased
Hyponatraemia	Hyponatraemia, Blood sodium decreased
Hypokalaemia	Hypokalaemia, Blood potassium decreased
Catheter site related reaction	Catheter site pain, Catheter site related reaction, Catheter site haemorrhage, Catheter site erythema, Catheter site bruise, Catheter site pruritus, Catheter site rash, Catheter site oedema, Catheter site discharge, Catheter site swelling
Abdominal pain	Abdominal pain, Abdominal tenderness, Abdominal pain lower, Abdominal pain upper
Sepsis/Bacteraemia	Sepsis, Bacteraemia, Enterococcal bacteraemia, Escherichia sepsis, Pseudomonal sepsis, Device related sepsis, Neutropenic sepsis, Staphylococcal bacteraemia

Grouped Term	Preferred Terms
Neuropathy peripheral	Neuropathy peripheral, Peripheral sensory neuropathy

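### AE and SAE collection opens only at the first infusion, so pre-dose complications of study procedures and of line placement go unreported unless they worsen after dosing

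*Protocol*

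**What the plan says.** **Collection window.** Protocol 7.2 collects information "on AEs during the period from the start of investigational drug administration to the end of follow-up period". Section 7.1.1 defines an AE as "any untoward medical occurrence in a subject administered an investigational drug". Section 7.1.2 makes an SAE a kind of AE, and 7.4 requires an initial report within 24 hours without stating a start date of its own.

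**One route back in.** Section 7.1.1 counts as an AE "Obvious exacerbation of the pre-existing medical conditions; worsening in severity, increase in frequency, or extending of duration of the events", so a pre-dose event that clearly worsens after dosing is captured.

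**Procedures before dosing.** Section 6.14.1 places contrast-enhanced CT, FDG-PET, bone-marrow biopsy or aspiration and, for subjects with a gastrointestinal lesion, endoscopy with biopsy in screening. Section 5.3.2 states that "administration of the investigational drug is recommended to be given through the central vein", through a port, central venous catheter or peripherally inserted line, because of injection-site problems seen with peripheral infusion.

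**What is recorded earlier.** Section 6.12 collects concomitant medication and procedures "from the day of obtaining the informed consent to the end of the follow-up period". Section 4.2.1 records admission and discharge dates over the study period, which includes screening.

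**Analysis.** The safety set in Protocol 9.1.3 is "A group of subjects who receive at least one dose of investigational drug". SAP 12.1.7 pools preferred terms into grouped rows. One of them begins "Catheter site pain, Catheter site related reaction, Catheter site haemorrhage, Catheter site erythema" and also includes bruise and swelling.

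**The concern.** The trial asks for invasive procedures in screening and recommends a route of infusion that may require placing a line. A line used for the first infusion is in place before AE collection opens. Haemorrhage, infection or a contrast reaction in that interval can be a consequence of taking part, yet the protocol gives it no place in the AE or SAE system.

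Two things are at stake. The first is subject protection: a life-threatening complication of a study biopsy before dosing triggers no 24-hour report to the sponsor under 7.4. The second is harm reporting. SAP 12.1.7 has an injection-site row and a catheter-site row, which readers are likely to set side by side as the local harm of the two routes. Peripheral reactions to the infusion start after dosing and are counted. Pain, bruising or bleeding from inserting a central line can start before dosing and is not. Any omission would favour the route that the protocol recommends.

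**Working it through.** **1. Length of the gap.** Inputs from Protocol 2.7.1: screening up to 28 days, 21 days per cycle, 21 days of follow-up, and a stated total of 175 days for six cycles.

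- Reproduce the plan's figure: 28 + 6 × 21 + 21 = 175 days = 25 weeks. It matches.
- AE window: 6 × 21 + 21 = 147 days.
- Outside the window: 175 − 147 = 28 days at most, and 28/175 = 16%.

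**2. Where a pre-dose complication would go.** Take a bleed after a screening marrow biopsy, with onset and resolution before the first infusion.

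| Record | Does it hold the event? |
|---|---|
| AE form (7.1.1, 7.2) | No: before first dose |
| SAE report (7.4) | No: an SAE must first be an AE |
| Concomitant medication and procedures (6.12) | The treatment and its indication; no severity, seriousness or outcome |
| Hospitalization (4.2.1; SAP 13) | Dates, if admitted |
| Medical history (6.5) | Collected on any one day in screening; before first dose, only whether a concurrent disease is ongoing |
| Withdrawal (4.4; SAP 10.1.3, 13) | A reason, for enrolled subjects; the criteria in 4.4.2 have no AE category |
| Safety tables (SAP 12) | No; a subject never dosed is also outside the safety set |

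If the complication prevents dosing, 4.4.3 requires no further examinations. If it prevents enrolment, which follows screening (4.3.2), the SAP shows only a count of subjects not enrolled (10.1.1).

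**3. Possible effect on the catheter-site row.** The documents give neither the frequency nor the timing of line placement, and no complication rate. As an assumption, let c be the share of 65 dosed subjects whose line is placed after consent and before first dose, and r the risk per placement of a catheter-site event that starts before dosing and does not worsen afterwards. Expected subjects omitted = 65 × c × r.

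| c | r | Subjects omitted | Percentage points of 65 |
|---|---|---|---|
| 10% | 1% | 65 × 0.10 × 0.01 = 0.07 | 0.1 |
| 50% | 5% | 65 × 0.50 × 0.05 = 1.6 | 2.5 |
| 90% | 10% | 65 × 0.90 × 0.10 = 5.9 | 9.0 |

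For given c and r this is an upper figure, because a subject who also has a catheter-site event after dosing is already in the row. Biopsy, endoscopy and contrast complications are separate and would not enter this row. Subjects never dosed come on top of the 65, because 4.5 keeps recruitment open until the planned number have received at least one cycle.

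**The case against.** A first-dose start agrees with the protocol's own definition of an AE, so this is a choice of scope and not a contradiction. It leaves the response rate, the sample size and the drug-related AE tables untouched. That stands.

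A reader might infer that the catheter-site row is understated as a matter of fact. The documents do not support this. Central access is recommended, not required. No time of placement is given, and 5.3.2 allows a switch to central access after a peripheral problem during infusion. Every subject has had prior treatment, so some may already have a line at consent. Catheter-site events with onset after first dose are counted through all cycles and follow-up. The row is correct for its window, and SAP 12.1.7 does not say that it measures harm of insertion.

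A reader might also infer that the plan would report none of these events, or that every screening procedure is imposed by the trial. Neither holds. Worsening after dosing is an AE. Protocol 6 allows marrow, CT and PET data from routine care before consent to be reused, and endoscopy applies only to gastrointestinal lesions. Nor are pre-dose harms wholly invisible: treatment, admissions and withdrawals are recorded and listed.

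Timing also counts against a purely prospective change. Protocol version 3.5 is dated January 2020. Survival surveillance lasts up to two years from first dose and is planned to end in December 2021. If that plan held, the last first dose was around December 2019 and screening was already over.

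What survives is the absence of any AE or SAE report for the event itself. A treatment entry or a hospital date does not give its severity, seriousness, cause or outcome.

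**Conclusion.** The gap is real and follows directly from 7.1.1, 7.2 and 7.4. Complications of study screening procedures, or of a line placed to give SP-02L, with onset between consent and first dose, are neither AEs nor SAEs in this trial unless they worsen after dosing. Other records hold only indirect traces. The missing SAE reporting is the stronger reason to act, and it does not depend on any assumed rate.

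The grouped catheter-site row covers onset after first dose and may understate total catheter harm. Whether it does, and by how much, cannot be settled from the documents. The range from near zero to about 6 of 65 subjects rests entirely on the assumed c (10% to 90%) and r (1% to 10%). It should not be quoted as an estimate.

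**What to change.** - **Protocol 7.1.1, 7.2 and 7.4, together.** Collect and report from informed consent all SAEs, and any AE that the investigator attributes to a study procedure, including line placement for SP-02L. Changing 7.2 alone would not work, because 7.1.1 would still exclude subjects not yet dosed.
- **SAP, one new table or listing.** Flag these events as pre-dose and show them over enrolled subjects, including those never dosed. Because screening precedes enrolment, list events in consented subjects who were not enrolled beneath it.
- **SAP 12.1.7 and the other treatment-emergent tables.** Keep the start at first infusion, do not add pre-dose events, and label the catheter-site row as onset after first dose. Adding pre-dose events to that one row would give it a different window from the rest.
- **Where screening is already complete.** List the pre-dose procedural events that can be identified from the concomitant medication and procedure, hospitalization and withdrawal records, and state that this source is incomplete.

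The cost is a short protocol and eCRF amendment, a little more data entry in screening, and one small table. No efficacy, alpha or power figure changes.
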